3.2 Analysis Populations

3.2.1 Intent-to-Treat (ITT) Population

The ITT Population will include all participants who are randomized into the study. Treatment classification will be based on the randomized treatment.

3.2.2 The Full Analysis Set (FAS)

The FAS will include all participants who are randomized into the study, take any study drug, and have at least 1 post-treatment lipid data assessment. Treatment classification will be based on the randomized treatment.

3.2.3 *Modified Intent-to-Treat (mITT) Population*

The mITT Population will include all randomized participants who receive at least 1 dose of any study drug and have data for both the Day 1 and Day 84 LDL-C assessments. Treatment classification will be based on the randomized treatment.

3.2.4 *Modified Intent-to-Treat (mITT) On-Treatment Population*

The mITT On-Treatment Population will include all randomized participants who, have data for both the Day 1 and Day 84 LDL-C assessments. Participants in the obicetrapib group with PK values less than 3 standard deviations from the mean obicetrapib concentration should be excluded. Treatment classification will be based on the randomized treatment.

Rationale: in previous studies, such as ROSE (protocol number TA-8995-201) and TULIP (protocol number TA-8995-03), and ROSE2 (protocol number TA-8995-202), it was demonstrated that the minimally observed obicetrapib concentration for C_{max} was less than three standard deviations from the mean at respectively Week 4 and Week 12 [3-5].

3.2.5 *Per-Protocol (PP) Population*

The PP Population will include all participants in the mITT Population who did not experience a major protocol deviation that potentially impacted the primary efficacy endpoint. The PP Population, along with the reason for exclusion, will be finalized prior to study unblinding.

3.2.6 *Safety Population*

The Safety Population will include all participants who receive at least 1 dose of any study drug. Treatment classification will be based on the actual treatment received. The Safety Population will be the primary population used for the safety analyses.

3.2.7 *24-hours ABPM Population*

The 24-hour ABPM Population will include all participants in the ITT Population who received at least 1 dose of any study drug and have valid data for both the baseline and Day 270 24-hour ABPM assessments and have 80% to 120% treatment compliance.

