3. Informed consent will be obtained from participants before the initiation of any study-specific procedures. In order to participate in the ABPM substudy, participants must provide written informed consent in a substudy-specific ICF.
4. Assessment of laboratory eligibility criteria will be based on central laboratory values obtained within timeframes defined in the inclusion and exclusion criteria.
5. Urine pregnancy tests will be performed for females of childbearing potential only (performed locally using central laboratory kit supplies). FSH will only be performed at Screening (Visit 1) in females <55 years of age and postmenopausal, defined as ≥1 year since their last menstrual period.
6. The physical examination should comprise a focused examination, which includes general, respiratory, CV, abdominal, and extremities evaluations; ophthalmological examination, and recording of weight and height.
7. Height will be measured at Screening (Visit 1) only and used to calculate BMI.
8. Vital signs (consisting of heart rate and blood pressure) will be measured as described in the clinical study protocol Section 8.9.
9. Only participants who consent to participate in the ABPM substudy will have this assessment performed.
10. The 24-hour ABPM assessment at Screening (Visit 1) should be completed after the participant's eligibility has been confirmed at that visit. It should be ensured that sufficient time is allotted during Screening (Visit 1) to allow for a repeat 24-hour ABPM assessment, if the first is not successful, prior to Visit 2. Additional details surrounding this substudy are included in a separate study manual.
11. It should be ensured that a repeat assessment (if necessary) is completed within the respective visit window and that the assessment is not done concurrently with other study procedures.
12. A single 12-lead ECG will be performed in the supine position after 10 minutes of rest.
13. Participants must fast for a minimum of 8 hours prior to samples being collected.
14. Samples should be collected prior to study drug administration.
15. Serum archive sample is not collected in China.
16. Only hsCRP will be assessed at Screening (Visit 1).
17. Urine dipstick analysis will be performed locally from a sample of mid-stream urine. In case of abnormal results, microscopy and other assessments will be performed at the local laboratory and the abnormality recorded as an AE.

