18. A PK sample will be collected prior to study drug administration for trough measurement of obicetrapib in plasma. At Visits 2, 5, and 7, participants should take study drug after a trough PK sample has been drawn.
19. CV events include CV death, non-fatal myocardial infarction, non-fatal stroke, non-elective coronary revascularization, hospitalization for unstable angina and/or chest pain, hospitalization for heart failure, and transient ischemic attack.
20. The PK sample at Visit 4 is not designated in the protocol, however the PK will be assessed using residual serum from the Day 84 limited chemistry panel to confirm participants are taking study drug.

ABPM = ambulatory blood pressure monitoring; AE = adverse event; ApoA1 = apolipoprotein A1; BMI = body mass index; CV = cardiovascular; ECG = electrocardiogram; EOS = End of Study; EOT = End of Treatment; ET = Early Termination; FSH = follicle-stimulating hormone; HOMA-IR = homeostatic model

assessment of insulin resistance; hsCRP = high sensitivity C-reactive protein; ICF = informed consent form; Lp(a) = lipoprotein (a); PK = pharmacokinetic(s); TSH = thyroid-stimulating hormone; UACR = urine albumin-creatinine ratio; UPCR = urine protein-creatinine ratio; V = Visit.

2.2.2 *Sample Size Determination*

Enrollment of approximately 2400 participants globally is planned for this study.

Assuming an approximate 5% drop out rate, approximately 2280 participants will be evaluable for efficacy. This sample size of at least 2280 evaluable participants will provide more than 90% power to detect a 30% reduction of LDL-C (standard deviation 15%) levels in the obicetrapib group compared to the placebo group at a 1-sided significance level of 0.025. This sample size will also contribute to sufficient participant exposure and safety data.

ABPM substudy

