3.3 Subject Data and Study Conduct

3.3.1 *Participant Disposition*

Counts and percentages of subjects who were randomized, completed the treatment period, discontinued treatment (including primary reason for discontinuation), completed the study, and prematurely discontinued from the study (including primary reason for discontinuation) will be summarized by treatment group and overall.

For each scheduled visit, counts and percentages of subjects who did not complete the visit, partially completed the visit in-person, or completed the visit via virtual method will be summarized by treatment group and overall. The denominator for calculating percentages will be based on the number of randomized participants.

Participants disposition and exclusion and inclusion criteria violations will be listed.

3.3.2 *Protocol Deviations*

Protocol deviations will be identified based on clinical data as defined in the Protocol Deviation Plan, where all protocol deviations will be defined as either CSR reportable or non-CSR reportable deviations. The CSR reportable protocol deviations will be categorized and separated by treatment group. The CSR reportable deviations will include all randomized subjects using counts and percentages.

A listing of CSR-reportable protocol deviations will be generated.

3.3.3 *Analysis Populations*

Counts and percentages of subjects in each analysis population will be summarized by treatment group and in total based on all randomized subjects. Reasons for exclusion from PP Population will also be summarized.

3.3.4 *Demographic and Baseline Characteristics*

The following demographic and baseline characteristics will be summarized with descriptive statistics or counts and percentages of subjects as appropriate by treatment group and overall, for the ITT Population:

- Age and age categories (<65 years, 65 to 74 years, and 75+ years)
- Sex
- Race
- Ethnicity
- Height
- Weight
- Body Mass Index (BMI)
- Region (Asia, Eastern Europe, Western Europe and North America)
- Country (USA, Japan, China, Other)
- Diabetes (yes, no)
- HDL-C (<40mg/dL, 40 - <60 mg/dL, ≥60mg/dL)
- ApoB (<60mg/dL, 60 - <90 mg/dL, ≥90mg/dL)
- ApoA1 (<110 mg/dL, ≥110 and <125 mg/dL, ≥125mg/dL)
- Lipoprotein(a) (<75nmol/L, ≥75 and <125 nmol/L, ≥125nmol/L)
- Non-HDL-C (<100 mg/dL, ≥100 and <130 mg/dL, ≥130mg/dL)
- LDL-C (<70mg/dL, ≥70 and <100 mg/dL, ≥100mg/dL)
- TG (<150 mg/dL, ≥150mg/dL)
- HbA1c (<5.7%, ≥5.7 to ≤6.4%, >6.4%)

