3.4 Efficacy Assessment

The ITT Population will be the primary population for the efficacy analysis. Efficacy will also be analyzed using the FAS, mITT Population, mITT On-Treatment Population, and PP Population as supportive analyses.

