Supplemental analyses will be performed for the primary efficacy endpoint in order to assess any differences with the results from the primary analysis and investigate what effect, if any, protocol violations have on the trial results. In the first supplemental analysis, a mixed model for repeated measures (MMRM) approach will be utilized. The LDL-C values measured by preparative ultracentrifugation will be used. The analysis will include fixed effects for treatment group, visit, and treatment-by-visit interaction, along with covariates of the Baseline LDL-C value as a continuous covariate, CV risk (HeFH or non-HeFH), Baseline statin therapy (HIS or non-HIS). The restricted maximum likelihood estimation approach will be used with an unstructured covariance matrix. The LS mean, standard errors, and 2-sided 95% confidence intervals for the treatment group and for the comparison of the treatment group to the placebo group will be provided. The MMRM approach will include all available assessments of percent change in LDL-C from Day 1, Day 30, Day 84, Day 180, Day 270, and Day 365. The model assumes that the data are missing at random (MAR). If any data are missing, the model will use all information from the other time points to estimate the mean treatment difference at the given time point. No imputation of missing data will be performed. The analysis will be conducted for ITT Population.

The analysis will be implemented using SAS® Proc Mixed. The sample SAS code can be found below:

Note:

USUBJID = unique subject identifier
TREATMENT = 0 (Placebo), 1 (Obicetrapib)
VISIT = visit
LDLC_BASE = Baseline LDL_C value
PCHG = Percent change from Baseline
CVRISK = 1 (HeFH), 0 (non-HeFH)
STATIN = 1 (HIS), 0 (non-HIS)

```
proc mixed;
  class USUBJID TREATMENT VISIT CVRISK STATIN;
  model PCHG = TREATMENT LDLC_BASE CVRISK STATIN VISIT TREATMENT*VISIT / solution cl;
  Repeated VISIT / TYPE=UN sub=USUBJID;
  lsmeans VISIT*TREATMENT / cl diff;
```

run;

Additional supplementary analysis will be performed using the ANCOVA model from the primary analysis based on the FAS, MITT, MITT On Treatment, and PP populations. No imputation for missing data will be performed for the analysis.

Secondary Estimand

A secondary estimand will be assessed for the primary efficacy endpoint. The secondary estimand is defined by the following key attributes:

- **Treatment:** obicetrapib versus placebo
- **Target Population:** participants who are randomized into the study

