5.2 Pre-Final Analysis

After the database is locked and exclusions from analysis populations have been finalized, the randomized treatment assignments will be unblinded and the pre-final analysis will be generated. Pre-final tables, figures, and listings (TFLs) will be provided approximately 3 weeks after database lock.

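### The PK exclusion rule for the mITT On-Treatment Population runs the wrong way as written, and the evident correction (below mean minus 3 SD) can fail to remove non-takers if concentrations are variable enough

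*SAP*

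**What the plan says.** SAP 3.2.4 builds the population from randomized participants with LDL-C at Day 1 and Day 84, then applies a filter to one arm: "Participants in the obicetrapib group with PK values less than 3 standard deviations from the mean obicetrapib concentration should be excluded". It names no visit, scale or direction, and no sample from which the mean and SD are taken. Its rationale says that in earlier obicetrapib studies the lowest observed Cmax "was less than three standard deviations from the mean at respectively Week 4 and Week 12".

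The purpose appears in Table 1, footnote 20, on the added Visit 4 measurement: "the PK will be assessed using residual serum from the Day 84 limited chemistry panel to confirm participants are taking study drug". Footnote 14, attached to the limited chemistry row, makes that sample pre-dose: "Samples should be collected prior to study drug administration".

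On use, SAP 3.4 says: "Efficacy will also be analyzed using the FAS, mITT Population, mITT On-Treatment Population, and PP Population as supportive analyses". The supplemental analyses in 3.4.1 apply the "ANCOVA model from the primary analysis based on the FAS, MITT, MITT On Treatment, and PP populations", without imputation, and 3.3.7 summarizes exposure in this population. On timing, 5.2 says: "After the database is locked and exclusions from analysis populations have been finalized, the randomized treatment assignments will be unblinded". Protocol 9.1 does not contain this population, and SAP 7 leaves programming detail to another document, so 3.2.4 is the only definition available.

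**The concern.** The sentence uses a distance from the mean where it needs a direction. A participant who takes the tablets and has an ordinary concentration lies less than 3 SD from the mean, so the plain words remove the people the population is meant to keep. The rationale does not settle the matter, because it uses the same phrase for participants in earlier studies.

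The natural repair is to drop values below mean minus 3 SD. Concentrations cannot be negative, so this cut-off works only if the spread is small relative to the mean. If the mean and SD come from the whole obicetrapib arm, non-takers lower the mean and raise the SD, and can hide themselves. A population labelled on-treatment would then still contain participants with no drug in their blood, and its estimate would be pulled toward no effect.

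**Working it through.** The documents give no count, mean, SD or CV for obicetrapib concentration, so there is no stated figure to reproduce.

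**Inputs from the documents.** Evaluable participants 2280, effect 30 points and SD 15 points (SAP 2.2.2); allocation 2:1 (SAP 2.2.1). Obicetrapib arm: 2/3 × 2280 = 1520; placebo arm: 760.

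**Literal rule, mean and SD from the values being filtered.** By Chebyshev's inequality, at most 1/9 of values lie 3 SD or more from their mean, whatever the distribution. 1520/9 = 168.9, so at most 168 stay and at least 1520 − 168 = 1352 go (88.9%). For normal data the share removed is 99.7%; for log-normal data with an assumed CV of 10% to 100% it is about 98.1% to 99.6%.

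The bound needs that internal reference. With an external Cmax reference the share can be much lower. As one illustration, with every input assumed: if the pre-dose mean is 40% of the reference mean, the reference SD is 20% of that mean and the taker CV is 20%, the rule removes about 46%.

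**Lower-tail rule, raw scale.** Cut-off = mean − 3 SD = mean × (1 − 3 × CV).

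| Total CV | Cut-off as share of mean |
|---|---|
| 10% | 0.70 |
| 20% | 0.40 |
| 30% | 0.10 |
| 33.3% | 0 |
| 40% | −0.20 |
| 50% | −0.50 |

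From 33.3% upward nobody is removed, not even a participant with zero concentration.

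**Masking.** Let a share p of the reference sample be non-takers at zero, and let c be the CV among takers. Then total CV = √[(1 + c²)/(1 − p) − 1]. Requiring this to be below 1/3 gives c < √[(10/9)(1 − p) − 1].

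| Non-takers p (assumed) | A zero is removed only if taker CV is below |
|---|---|
| 0% | 33.3% |
| 1% | 31.6% |
| 2% | 29.8% |
| 5% | 23.6% |
| 8% | 14.9% |
| 10% or more | no value works |

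For example, with c = 20%, p = 5% gives √(1.04/0.95 − 1) = 30.8% and non-takers are removed; p = 10% gives √(1.04/0.90 − 1) = 39.4% and none are. If the convention in SAP 3.1.9 of replacing values below quantification by half the limit also covers PK, which is an assumption, the rule fails at a slightly lower CV.

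**Log scale.** The cut-off stays positive (0.36 of the mean at CV 33.3%, 0.22 at 50%), but masking can persist. In simulations with non-takers set at 1% of the taker mean (assumed), and mean and SD from the mixed arm, all were removed at 1% to 5% non-takers and none at 10%.

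**Effect on the estimate if nobody is removed.** Assume non-takers respond like placebo. Dilution = 30 × p: 0.3, 0.6, 1.5 and 3.0 points at p = 1%, 2%, 5% and 10%. For scale, the standard error is 15 × √(1/1520 + 1/760) = 0.67 points.

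**The case against.** The best defence is that no programmer would implement the literal reading. Footnote 20 makes the aim plain, and an almost empty obicetrapib arm would be seen at once, because under SAP 3.3.3: "Counts and percentages of subjects in each analysis population will be summarized by treatment group and in total based on all randomized subjects". This stands as far as it goes: the literal figures describe what the words say, not what is likely to be run. The words still need correcting, because they are the only definition.

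A reader might infer that correcting the direction is bound to fail. The documents do not support that. Failure requires the raw scale and a total CV of at least 33.3%, and the SAP states neither. The rationale gives no evidence of a high CV. If earlier minima lay within 3 SD of the mean, it says nothing about the CV. If they lay below mean minus 3 SD on the raw scale, it implies a CV under 33.3% in those studies. Either way it concerns Cmax, not the pre-dose sample used here.

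A reader might also infer that a lower-tail failure would go unnoticed, since zero exclusions resembles full adherence. That is too strong. Day 84 concentrations are an exploratory endpoint (2.3.3) and are summarized descriptively (3.4.3), generally with mean, SD and minimum (3.1.5), and 3.3.7 tabulates compliance. Mean minus 3 SD could be read from those tables. What remains is timing: they are produced after unblinding, when a change to the rule would be post hoc.

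Finally, the consequence is modest. Retained non-takers pull the estimate toward the null, by less than one standard error at 1% to 2%; even 10% leaves 27 of the planned 30 points.

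**Conclusion.** The rule is wrong as written. Its plain meaning excludes values within 3 SD of the mean, at least 1352 of 1520 evaluable obicetrapib participants if the mean and SD come from those same values, and this contradicts the purpose in footnote 20. That part rests on the text and a distribution-free bound.

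The second part is conditional. A direction-corrected rule on the raw scale removes nobody once total CV is 33.3% or more, and non-takers in the reference sample bring that point closer. The algebra is exact, but the CV, the scale, the reference sample and the share of non-takers are not in the documents, so whether it would happen in this trial is unknown. The dilution figures also assume that non-takers respond like placebo.

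This should be fixed, but it does not threaten the trial. A reader might take it as a doubt about the main result; it is not one, because the primary ITT analysis does not use this population. Only supportive efficacy analyses and one exposure summary do.

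**What to change.** Before unblinding, amend SAP 3.2.4 to correct the direction and replace the SD rule with one that non-takers cannot mask. For example: exclude an obicetrapib participant whose Day 84 concentration is below the assay's lower limit of quantification. A fixed concentration, or a log-scale limit from confirmed takers or earlier pre-dose data, would also serve, but the documents show no data from which to set either. Name the visit. State how a missing Day 84 PK result is handled, report how many are missing, and show the result with those participants in and out.

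The rule must be squared with SAP 5.2, which closes population exclusions before unblinding, while this rule needs the arm and concentrations would themselves reveal it. One way is to fix the rule in advance, have an unblinded PK or programming function flag samples below the cut-off before unblinding, and apply arm membership by program when the codes are released.

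The cost is SAP wording and a table row; the Day 84 assay is already planned. The downside is that a quantification-limit rule misses partial adherence and keeps participants who stopped recently but still have measurable drug. The filter also acts on one arm only, so the report should say that the comparison is not a randomized one.

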## APPENDIX E: CORRECTION FACTORS FOR LIPID-MODIFYING DRUGS

Lipid-Modifying Drug		
Dose	Reduction in Percentage	Correction Factor 
Atorvastatin		
10 mg	37	1.59
20 mg	43	1.75
40 mg	49	1.96
80 mg	55	2.22
Fluvastatin		
20 mg	21	1.27
40 mg	27	1.37
80 mg	33	1.49
Pravastatin		
10 mg	20	1.25
20 mg	24	1.32
40 mg	39	1.64
Rosuvastatin		
5 mg	38	1.61
10 mg	43	1.75
20 mg	48	1.92
40 mg	53	2.13
Simvastatin		
5 mg	23	1.30
10 mg	27	1.37
20 mg	32	1.47
40 mg	37	1.59
Statin/Ezetimibe		
Low-dose/10 mg	44	1.79
Mid-dose/10 mg	45	1.81
High-dose/10 mg	53	2.13
Ezetimibe		
10 mg	19	1.23

Correction factor = 100/(100 - reduction in percentage).

Sources

2004;58(8):746-755

Davidson MH, Ballantyne CM, Kerzner B, et al. Efficacy and safety of ezetimibe coadministered with statins: randomised, placebo-controlled, blinded experience in 2382 patients with primary hypercholesterolemia. *Int J Clin Pract*.

Source: Besseling J, Kindt I, Hof M, et al. Severe heterozygous familial hypercholesterolemia and risk for cardiovascular disease: a study of a cohort of 14,000 mutation carriers. *Atherosclerosis*. 2014;233(1):219-223

1. The correction factor should be multiplied by a historical or Screening LDL-C value. For example, a patient taking atorvastatin 80 mg, with an LDL-C of 93 mg/dL, has the equivalent of an "off-treatment" LDL-C value of 206.46 mg/dL (93 mg/dL × 2.22 = 206.46 mg/dL).

LDL-C = low-density lipoprotein cholesterol.

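### The on-treatment LDL-C analysis filters by drug concentration in the obicetrapib arm only, so this supportive comparison is not protected by randomization and may be biased

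*SAP*

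**What the plan says.** SAP 3.2.4 defines the set in two steps. The base is common to both arms: "The mITT On-Treatment Population will include all randomized participants who, have data for both the Day 1 and Day 84 LDL-C assessments". The exclusion is not. It is addressed only to "Participants in the obicetrapib group with PK values" that fail a cut-off, and in full it reads: "Participants in the obicetrapib group with PK values less than 3 standard deviations from the mean obicetrapib concentration should be excluded". Nothing corresponds to it for placebo. The parent set in SAP 3.2.3 at least requires dosing ("The mITT Population will include all randomized participants who receive at least 1 dose of any study drug"), and that condition is missing from the on-treatment set.

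The Day 84 concentration comes from a footnote to the SAP's schedule of procedures: "the PK will be assessed using residual serum from the Day 84 limited chemistry panel to confirm participants are taking study drug". The rationale for the cut-off cites peak concentrations in earlier studies, where the lowest value "was less than three standard deviations from the mean at respectively Week 4 and Week 12".

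SAP 3.4 gives the set its role: "Efficacy will also be analyzed using the FAS, mITT Population, mITT On-Treatment Population, and PP Population as supportive analyses". SAP 3.4.1 specifies the primary ANCOVA on observed data without imputation for these populations. The primary analysis itself is ITT under a treatment policy strategy with multiple imputation. The on-treatment set is not among the populations in Protocol 9.1 or the changes listed in SAP Section 6.

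**The concern.** Two people who stop their tablets are treated differently according to their arm. The one on obicetrapib is meant to be removed by the concentration check. The one on placebo stays in if Day 1 and Day 84 LDL-C are available. Such placebo participants will be present, because Protocol 4.3 asks people who stop study drug to keep attending visits.

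This matters if people who abandon study tablets also tend to abandon their background statin. Protocol 5.6.3 records statin discontinuations, so the sponsor foresees some. Placebo would then keep participants whose LDL-C rises for that reason, while the obicetrapib arm loses them. At stake is the size of the effect reported for people who take the drug, which readers may set beside the ITT estimate as confirmation.

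**Working it through.** **Planned precision.** The documents give no figure for the on-treatment analysis, so I start from the primary sample size (Protocol 9.2.6, SAP 2.2.2): 2400 × 0.95 = 2280 evaluable, which at 2:1 is 1520 and 760. With SD 15, SE = 15 × √(1/760 + 1/1520) = 0.67 points. A 30-point difference is about 45 standard errors, so the stated power above 90% is reproduced (it is essentially 100%).

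**Model.** Let q be the share of non-takers in each arm among those with Day 84 LDL-C. Let s be the LDL-C percent change of non-takers minus that of takers, apart from any drug effect. Let the effect in takers be −30.

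- No filter: −30 × (1 − q).
- Same accurate filter in both arms: −30.
- Filter in the obicetrapib arm only, all non-takers removed: −30 − q × s.

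The bias is therefore q × s. If only a fraction f of non-takers is removed, the background part becomes q × f × s × (1 − q)/(1 − q × f). The last factor is close to 1 (0.95/0.975 = 0.97 at q = 5%, f = 0.5), so the bias is in effect the share excluded times s. At f = 0 it vanishes.

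**One-arm-filter estimate, in points** (q and s assumed; the documents give neither):

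| q | no filter | s = −10 | s = 0 | s = 10 | s = 20 | s = 30 |
|---|---|---|---|---|---|---|
| 1% | −29.7 | −29.9 | −30.0 | −30.1 | −30.2 | −30.3 |
| 2% | −29.4 | −29.8 | −30.0 | −30.2 | −30.4 | −30.6 |
| 5% | −28.5 | −29.5 | −30.0 | −30.5 | −31.0 | −31.5 |
| 10% | −27.0 | −29.0 | −30.0 | −31.0 | −32.0 | −33.0 |

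**A value of s from statin stopping.** Protocol Appendix E gives "Correction factor = 100/(100 - reduction in percentage"). For atorvastatin 40 and 80 mg the factors are 1.96 and 2.22, implying rises of 96% and 122% on stopping. If a share r of non-takers also stops, s = r × 96 to r × 122.

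- q = 5%, r = 30%: 0.05 × 0.30 × 96 = 1.44; with 122, 1.83.
- Low corner, q = 2%, r = 10%: 0.02 × 0.10 × 96 = 0.2.
- High corner, q = 10%, r = 50%: 0.10 × 0.50 × 122 = 6.1.
- Weaker statin, pravastatin 20 mg (factor 1.32), q = 5%, r = 30%: 0.05 × 0.30 × 32 = 0.5.

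Against the standard error, 1.44 to 1.83 points is 2.1 to 2.7 SE. If the drug had no effect, a nominal two-sided 5% comparison on this set would reject about 9% of the time at q = 2%, s = 20, and about 32% at q = 5%, s = 20.

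**Does the cut-off remove anyone?** Read literally, the rule excludes values within 3 SD of the mean, which is nearly everyone. Read as below mean minus 3 SD, using the arm's own mean and SD with non-takers at zero, the cut-off is positive only if 9 × CV² + 10 × q < 1, where CV is the takers' coefficient of variation. At CV 20% that needs q < (1 − 0.36)/10 = 6.4%. At CV 30% it needs q < (1 − 0.81)/10 = 1.9%. At a CV of one third or more it is never positive, so zero concentrations stay in and this bias does not arise. The SAP does not say whether the mean and SD come from this trial, which visit is used, or whether the scale is raw or log.

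**The case against.** The strongest reply is that neither direction nor size is established. No document gives data on background LDL-C change in non-takers. With s = 0, an on-treatment estimate larger than the mITT one is simply the effect in takers: at q = 5%, the move from −28.5 to −30.0 removes dilution and is not bias. That stands. A reader might infer that the filter exaggerates the drug effect, but the documents support only that it may.

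The size is also open to challenge. The 96% to 122% range applies to two doses of one statin, in factors meant for estimating untreated LDL-C at HeFH diagnosis. Up to 30% of participants may be off high-intensity statins and up to 10% may be statin intolerant. People who disengage entirely have no Day 84 LDL-C and are out of both arms, so the 5% dropout assumption does not supply q. The 6.1-point corner combines every unfavourable assumption. All of this stands, and the size is only illustrative.

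Third, the plan already has analyses that treat both arms alike: the hypothetical estimand, which drops values after discontinuation or prohibited medication in either arm, and the Per-Protocol Population. The on-treatment set is not a separate step in the SAP 3.4.2 testing sequence. This limits the consequence but does not repair the on-treatment comparison, which the SAP still presents as supportive.

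**Conclusion.** The point holds as a risk of bias in one supportive analysis. The one-arm exclusion is explicit in the SAP, and following it gives a comparison selected after randomization in one arm only. The bias favours obicetrapib if non-takers also tend to stop background statin: about 1 to 2 points if 5% are non-takers and 30% of those stop a high-intensity statin, both assumed. It is zero if non-takers and takers have the same background change or if the cut-off excludes nobody, and it reverses if non-takers do better.

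Two stronger inferences are unsupported. One is that the comparison uses every placebo participant; it uses those with Day 1 and Day 84 LDL-C, possibly including some who took no dose. The other is that the ITT finding is weakened; that analysis does not use this set. What is affected is how far the on-treatment estimate can be read as corroboration, and its exact value.

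**What to change.** In SAP 3.2.4 and 3.4.1, label the PK-filtered ANCOVA descriptive and state its cut-off explicitly (direction, source of mean and SD, visit, scale). For the on-treatment effect, add one of the following.

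1. The same adherence criterion in both arms, for example no discontinuation before Day 84 and the 80% to 120% tablet compliance already used for the ABPM population, calculated to Day 84. Tablet counts measure adherence imperfectly (SAP 3.3.7 counts unreturned tablets as taken), and selection can still differ between arms if treatment itself affects adherence.
2. A complier-average estimate: the between-arm difference among participants with observed Day 84 LDL-C, divided by the proportion of those in the obicetrapib arm with drug present, with a bootstrap confidence interval. In the model above, −28.5/0.95 = −30.0 at q = 5%, whatever s is. It should be restricted to observed Day 84 data, because concentration status comes from that visit's residual serum and is unknown where Day 84 is imputed. It assumes no effect of assignment in those without drug present, and comparable Day 84 missingness across arms. Partial or recent takers classed as drug-free would strain the first assumption.

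The cost is one SAP paragraph and a short program on data already planned.
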